## B. Outcomes study

This section describes the research questions, evaluation enrollment process, data collection procedures, outcome measures, and analytic approach for the outcomes study.

### 1. Research questions

RQ1.1: Did the multistep CQI process support changes in primary workshop dosage, program attrition rates, or survey response rates at the program level?

RQ2: Did meaningful improvements in primary workshop dosage, survey response rates, or program attrition rates vary by service site *for sites that focused on improving the same metrics?*

RQ3 [secondary]: Do participants report healthier partner relationship attitude outcomes after program participation, as compared to baseline?

RQ4 [secondary]: Was level of dosage associated with reporting healthier partner relationship attitude outcomes after program participation, as compared to baseline?

### 2. Outcomes evaluation enrollment

This study was initially approved by Solutions IRB on 03/29/2021 and has been annually reviewed and approved on 03/15/2022, 03/07/2023, and 3/11/2024. Additionally, revisions to the study were submitted as amendments and were approved on 05/17/2022, 02/15/2023, and 08/29/2023.

Participants for the program, and thus the study, are recruited primarily from community partnerships, walk-ins to Anthem Strong Families, radio and social media advertising, and word of mouth referrals.

Program service locations have varied throughout the implementation of the program but have included:

---

- Schools
  - Stephen C. Foster Elementary School
  - Herbert Marcus Elementary School
  - Burnet Elementary School
- Treatment Centers / Transitional Facilities
  - Soul's Harbor Treatment Center
  - Free Man House Transitional Living Facility
  - Shurrun's House Sober Living Facility
  - Gateway Foundation Treatment Center
- Vickery Meadow Youth Development Foundation
- Buckner Children and Family Services, Family Hope Center at Bachman Lake
- Virtual services provided via Zoom

The projected enrollment and desired sample size for the study is 800 participants. The final report will include a breakdown of the number of sites, number of staff at each site, and number of participants at each site.

To be eligible for the program, and thus the study, participants must be 1) low-income individuals, 2) at least 18 years of age, 3) with no open criminal cases (can be deferred), and 4) able to speak and understand English or Spanish.

Consent for enrollment into the evaluation happens during program orientation, prior to the start of the first primary workshop. A consent form is provided to participants, and a script is read by either the facilitator or the data manager, explaining the study activities and the potential risks and benefits. Participants sign and date the consent form and return it to the data manager, who logs the record in a consent spreadsheet on MER's secure Dropbox.

Enrollment into the study began April 22, 2021 and is estimated to conclude February 15, 2025.

### **3. Data sources and data collection**

The data source for the program implementation and performance outcome measures is nFORM administrative data. Program staff are responsible for entering and updating client and workshop information, including workshop attendance and current client status, on an ongoing basis. These data are summarized bi-weekly in Step 1 CQI reports with metrics at the program level and annually in Step 2-4 CQI reports with metrics at the site level to monitor trends in program enrollment, workshop dosage, program attrition rates, and survey response rates.

The data source for participant outcomes related to healthy partner relationship attitudes is the nFORM

Healthy Marriage Adult Program survey, administered at orientation before the first primary workshop (entrance survey) and at the final primary workshop session (exit survey).

**Table 3.** Sources of data to address the research questions

Data source	Timing of data collection	Mode of data collection	Start and end date of data collection
nFORM administrative data	Ongoing	Program staff enter and update data related to enrollment, attendance, and client status	Start: April 2021 End: April 2025
nFORM Healthy Marriage Adult Program Survey	At orientation before the first primary workshop (entrance survey) and at the end of the final primary workshop session (exit survey)	Online via tablet or on paper as necessary	Start: April 2021 End: April 2025

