**Family Champions Project
Statistical Analysis Plan**

Clinicaltrials.gov ID: NCT05298345

September 4, 2024

Analysis approach

To assess the association between the multistep CQI process and the outcome measures, trends in dosage, retention, and survey response rates will be assessed over time since the start of the program. If the CQI process has been effective in identifying and addressing issues that require intervention, we would expect that program implementation would get stronger over time, as measured by progress toward meeting programmatic targets for these measures.

Analytic sample

The analytic sample for RQ1 and RQ2 is made up of the participants who received services at the facilities that received CQI intervention efforts as part of the multistep CQI process. The aggregated dosage, retention, and survey response rate data for these participants will make up the analytic sample.

The analytic sample for the secondary research questions (RQ3 and RQ4) about participant healthy partner relationship attitudes will be defined as participants who have complete baseline and outcome data for the constructed outcome measure (complete case). Because these relationship questions are only shown to participants who report currently being in a romantic relationship, participants can only have complete case survey data if they report being in a relationship at both waves of data collection. As mentioned above, participants will only be included in the analytic sample if they have one or no missing values for the five items used to construct this outcome measure (80% or 100% of non-missing items). Participants who do not meet this threshold will have their outcome value assigned to missing and will not be included in the analytic sample; no imputation is planned for the outcome data.

Data preparation

Program-level and participant-level data will be downloaded as an Excel file using nFORM's data export feature. The data sets will be cleaned and prepared for analysis using the R Studio statistical software package. All files will be exported into R and cleaned separately before data sets are merged into a final, wide format file for analyses using nFORM client ID as the unique identifier for matching programmatic (dosage, client status, survey response rates) and participant survey data.

Analytic approach

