The analysis for this evaluation will be completed using Excel and the R Studio statistical software package. Trends in programmatic outcome measures will be assessed descriptively over time using graphs that show average dosage, attrition, and survey response rates by month since program start among participants who enrolled in that month. Trends in program-level (cross-site) averages will be assessed for improvements over time, and trends in site-level averages will be assessed both for improvements since program start and immediately following the implementation of targeted interventions, which will be noted on the graphs. Site-level averages will be compared across the full study time period. Assuming the continuous, rapid cycle learning and intervention of the multistep CQI process is happening as planned, average metrics are expected to improve over time and immediately following interventions.

For the secondary research question 3 analysis, a change score will be calculated for each complete case respondent using their average at program entry and their average at program exit. We will use paired sample

t-tests to assess the magnitude and significance of mean score changes among program participants in the analytic sample. For the secondary research question 4 analysis, a basic regression model will be used to determine if higher dosage of primary workshop hours is associated with higher average scores on attitudinal items. Findings are considered statistically significant based on a $p < 0.05$, two-tailed test.

Attrition

Sample attrition is not a concern for the programmatic measures assessed for RQ1 and RQ2.

For the secondary research questions, sample attrition is related to program retention, as participants can only have complete case data if they stay in the program to take their nFORM exit survey. Anthem Strong Families staff have implemented numerous strategies to increase participant retention. Retention is tracked on an ongoing basis as part of the bi-weekly CQI team meetings between Anthem and MER staff, so decreases in survey response rates or participant retention can be tracked and addressed in real time as cohorts are enrolled in the program.

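### RQ4 relates attitudes to workshop dosage only among exit-survey takers, so the dosage range is truncated and the conclusion should be limited to it

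*Protocol*

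**What the plan says.** The protocol (Outcomes study, section 1) poses RQ4 as a secondary question: "Was level of dosage associated with reporting healthier partner relationship attitude outcomes after program participation, as compared to baseline". Table 4 measures dosage as the percentage of target workshop hours received. Table 1 sets those hours at 18, in six two-hour and two three-hour sessions.

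The attitude survey is given "at orientation before the first primary workshop (entrance survey) and at the final primary workshop session (exit survey") (protocol, Outcomes study, section 3). Table 3 places the exit survey at the end of that last session.

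The SAP, under Analytic sample, defines the RQ3 and RQ4 set as "participants who have complete baseline and outcome data for the constructed outcome measure (complete case") and adds that "no imputation is planned for the outcome data". There is a second filter, because "participants can only have complete case survey data if they report being in a relationship at both waves of data collection". Under Analytic approach, "a basic regression model will be used to determine if higher dosage of primary workshop hours is associated with higher average scores" on the attitude items. No covariate is named, and the only decision rule is a two-sided test at 0.05.

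Under Attrition, the SAP acknowledges that "participants can only have complete case data if they stay in the program to take their nFORM exit survey". Its response is staff retention efforts, plus a report of the proportion of enrollees missing the outcome, by reason.

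**The concern.** Staying to the last session is a large part of what determines dosage. Entry to the RQ4 sample therefore depends on the exposure that RQ4 studies. Early leavers supply much of the spread in dosage and contribute nothing to the regression, whereas the research question is about level of dosage without restriction.

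Three consequences follow. The slope is estimated over a compressed range and so imprecisely. Any benefit that separates very low from moderate dosage lies mostly outside the data. And if those who stay differ from those who leave in ways related to attitudes, the slope may be biased in either direction, which affects a positive finding as much as a null one. The SAP's missingness report gives reasons but does not compare dosage between included and excluded enrollees, so a reader could not see how much of the range is lost.

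**Working it through.** **Inputs from the documents.** Session hours 6×2 + 2×3 = 18, which reproduces the stated total. Exit survey at the final session. Complete cases, no imputation. Two-sided alpha 0.05. Projected enrollment 800, which cannot be reproduced because no effect size, SD or power is given.

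**Assumed inputs (the documents give none).** 10-40% leave early, at a uniformly random point; 70-95% attendance per session while enrolled; exit survey taken only if session 8 is attended; 40% or 60% in a relationship at both waves; full-range correlation r = 0.20.

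**Step 1: can low dosage occur in the sample?** Yes. Someone who attends only the last session has 3/18 = 16.7% of hours, or 2/18 = 11.1% if that session is a two-hour one. In simulations of 400,000 participants per scenario, 7-38% of all enrollees have under 50% dosage, against 0-3% of those surveyed at exit. Only 0-11% of the under-50% group take the exit survey. Low dosage is nearly, but not wholly, removed.

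**Step 2: range restriction.** Let u = SD(dosage among exit-surveyed) / SD(dosage among all). The restricted correlation is r′ = r·u / √(1 − r² + r²u²). Power is Φ(atanh(r′)·√(n − 3) − 1.96).

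With 30% leaving early and 85% attendance, u = 0.114/0.289 = 0.39 and r′ = 0.20×0.39/√(0.96 + 0.04×0.39²) = 0.08. At n = 300, power is Φ(0.080×17.23 − 1.96) = 0.28. With no restriction it is Φ(0.203×17.23 − 1.96) = 0.94.

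| Leave early | Attendance | SD all | SD exit | u | r′ | Power, n = 300 |
|---|---|---|---|---|---|---|
| 10% | 70% | 0.212 | 0.146 | 0.69 | 0.139 | 0.68 |
| 10% | 95% | 0.204 | 0.070 | 0.34 | 0.069 | 0.22 |
| 30% | 85% | 0.289 | 0.114 | 0.39 | 0.080 | 0.28 |
| 40% | 70% | 0.277 | 0.146 | 0.53 | 0.107 | 0.46 |
| 40% | 95% | 0.329 | 0.070 | 0.21 | 0.043 | 0.11 |

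The first and last rows are the extremes of the 12 scenarios examined.

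**Step 3: let n follow from 800.** Taking n = 800 × relationship share × share surveyed at exit gives 134 to 410, with power 0.08-0.68. If every enrollee in a relationship could be measured (n = 320 or 480), power would be 0.95-0.99.

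**Step 4: bias or imprecision?** Use 30% early leaving, 85% attendance and residual SD 0.7. With a linear effect of true slope 0.30, and selection depending only on attendance, the fitted slope is 0.31 in all enrollees and 0.28 in the exit-surveyed, which agree within simulation error. The standard error grows by (0.289/0.114) × √(1/0.60), about 3.3 times. If instead the benefit is a step of 0.3 at 50% dosage, the fitted slope falls from 0.38 to 0.02.

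**The case against.** The best defence is that the SAP already states the dependence on retention and promises missingness by reason, that RQ4 is secondary in a descriptive evaluation, and that under a linear effect the slope is essentially unbiased. All of that is true. It leaves open how dosage differs between included and excluded enrollees, and how far the conclusion may reach.

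Three stronger readings are tempting, and the documents do not support them.

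- A reader might infer that every low-dosage participant is excluded by design. Intermittent attenders who reach the end remain, with dosage possible down to 11-17%. Nor do the documents say whether someone absent from the last session may complete the exit survey later; if so, the truncation is milder.
- A reader might infer that the regression merely compares no missed sessions with one or two. That depends on assumed attendance: among final-session attenders, 0.95⁷ = 70% missed nothing at 95% attendance, but 0.70⁷ = 8% at 70%.
- A reader might infer that a non-significant slope will be reported as showing that dosage does not matter. No text says so; the SAP states only when a finding counts as significant.

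It can also be said that adjusting for the entry score does not cure truncation. That is right. It is recommended because RQ4 asks about outcomes relative to baseline and the SAP's model names no baseline term.

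**Conclusion.** The point holds as a limit on what RQ4 can conclude. Early leavers are structurally absent, most low-dosage enrollees are likely to be absent with them, and the plan neither shows nor allows for this.

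The size depends heavily on rates that the documents do not give. Over the assumed range, power at n = 300 is about 0.11-0.68 against 0.94 without restriction. Even the most favourable scenario stays below 0.80, so a null would be weak evidence against a dosage effect. The harm is mainly imprecision if the effect is linear and selection depends only on attendance. It is a missed effect if the benefit is concentrated at low dosage, and bias of unknown sign if retention is selective on attitudes. As a secondary question with an inexpensive remedy, it should be corrected, but it does not threaten the evaluation's main questions.

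**What to change.** In the RQ4 paragraph of the SAP:

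1. Specify a regression of the exit composite on dosage with the entry composite as a covariate, and report the dosage slope with a 95% CI.
2. Tabulate the dosage distribution for enrollees included in and excluded from the RQ4 sample. The attendance data are in nFORM, and the SAP already plans to merge them with the survey data by client ID.
3. State that the RQ4 conclusion, positive or null, applies to participants who took the exit survey and to the dosage range observed among them.

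No new data collection is needed. The cost is a few sentences, one extra table and a narrower secondary claim. The table would also show directly whether the truncation is severe or mild, replacing the assumed rates used here.

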#### 4. Outcome measures

The main outcomes of interest addressed by the multistep CQI process are primary workshop dosage, participant attrition rates, and nFORM survey response rates, as these are key program performance metrics with targets set by the federal funders. The first research question looks at changes in each of these metrics over time overall across all service sites (program level), and the second research question looks at changes in each of these metrics over time broken down by service site for sites that focused on the same metrics. This will involve an assessment of any changes in metrics after intervention strategies were implemented, including whether performance targets were reached and whether improvements were meaningfully large. Potential ceiling and floor effects are mitigated during the process of selecting which metrics to attempt to improve via intervention strategies (i.e., metrics that are already at or close to targets are not selected for intervention); however, potential ceiling and floor effects will also be addressed by providing baseline data for metrics targeted for interventions at each service site.

The secondary research questions about participant-level attitude changes after program participation are assessed by constructing a composite measure calculated as the average of five nFORM survey items related to partner trust and intimacy. If more than one survey item within the composite is missing for a respondent, the value of the outcome measure will be set to missing.

**Table 4.** Outcomes used to answer the research questions

Research question	Outcome name	Description of the outcome measure	Source of the measure	Timing of measure
RQ1	Dosage	The outcome measure is the percent of target primary workshop hours received by program participants	nFORM operational report: Primary Workshop Participation Detail	Attendance is recorded after each workshop session
RQ1	Attrition	The outcome measure is the percent of program participants who leave the program without completing at least 90% of primary workshop hours	nFORM operational report: Client Status Summary	Ongoing

Research question	Outcome name	Description of the outcome measure	Source of the measure	Timing of measure
RQ1	Survey response rates	The outcome measure is the percent of eligible participants who completed nFORM entrance and exit surveys	nFORM operational report: Survey Completion Summary	Ongoing
RQ2	Dosage	The outcome measure is the percent of target primary workshop hours received by program participants at each service site	nFORM operational report: Primary Workshop Participation Detail	Attendance is recorded after each workshop session
RQ2	Attrition	The outcome measure is the percent of program participants who leave the program without completing at least 90% of primary workshop hours at each service site	nFORM operational report: Client Status Summary	Ongoing
RQ2	Survey response rates	The outcome measure is the percent of eligible participants who completed nFORM entrance and exit surveys at each service site	nFORM operational report: Survey Completion Summary	Ongoing
RQ3	Healthy partner relationship attitudes	The outcome measure is a scale (value range 1-5) calculated as the average of five survey items measuring trust and intimacy	nFORM Healthy Marriage Adult Program survey D10.a-e (entrance and exit)	During orientation (entrance) and after the final workshop session (exit)
RQ4	Healthy partner relationship attitudes	The outcome measure is a scale (value range 1-5) calculated as the average of five survey items measuring trust and intimacy	nFORM Healthy Marriage Adult Program survey D10.a-e (entrance and exit)	During orientation (entrance) and after the final workshop session (exit)

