#### 2. **Step 2: Performance Intervention Priorities Report (prepared and presented annually in quarter 2 of each grant year by evaluation lead)**

- a. Report description – compare overall performance trends by service site
- b. Purpose – target improvement efforts by setting site-specific priorities for interventions
- c. Fidelity tracking -
  - i. Intended amount of CQI to be offered based on intended report timeline
  - ii. Actual amount offered (# CQI Team meetings scheduled for Step 2 Reports on Outlook, # CQI Team meetings where Step 2 CQI Report was presented to CQI Team, # Step 2 reports created)

---

- d. Dosage tracking –
  - i. Intended amount received – attendance of all members at CQI Team meetings for Step 2 Reports (i.e., number, names, roles)
  - ii. Actual amount received – CQI Tracking Sheet for Team Attendance (See Appendix B) for Step 2 Reports
- e. Feasibility Assessment –
  - i. Focus on utility and user-friendliness of Step 2 report
  - ii. CQI Team Survey for Step 2: administered each program year to staff on the CQI Team
  - iii. Family Champions Project staff survey for Step 2: administered each program year to all frontline staff who help to develop targeted, site-specific interventions during staff meetings with leadership and with the CQI team on a rotating basis

**3. Step 3: Performance Intervention Strategy Report (prepared for each service site in quarter 2 of each grant year by evaluation lead)**

- a. Report description – use key indicators to track performance trends for each site individually
- b. Purpose – establish a performance intervention agenda for each site
- c. Fidelity tracking –
  - i. Intended amount to be offered based on intended report timeline
  - ii. Actual amount offered (# CQI Team meetings scheduled on Outlook, # CQI Team meetings where Step 3 CQI Report presented to CQI Team, # Step 3 reports created)
- d. Dosage tracking –
  - i. Intended amount received – attendance of all members at CQI Team meetings for Step 3 Reports (i.e., number, names, roles)
  - ii. Actual amount received – CQI Tracking Sheet for Team Attendance for Step 3 Reports
- e. Feasibility assessment –
  - i. Focus on utility and user-friendliness of Step 3 report
  - ii. CQI Team Survey for Step 3: administered each program year to staff on the CQI Team

**4. Step 4: Performance Intervention Results Reports (prepared annually in quarter 4 of each grant year by evaluation lead)**

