CQI Process Step 4	Assessing the results of targeted interventions that were put in place at specific sites based on the findings of the Step 2 and Step 3 reports	Reports are prepared annually in the fourth quarter of each grant year and discussed at standing CQI team meetings	Existing CQI team meetings are used to present and discuss Step 4 report findings (e.g., did the targeted metrics improve after implementing interventions? Does the metric now meet relevant standards? Were there any challenges with the implementation of interventions? How did frontline staff, leadership, and facility staff find the intervention? ); the evaluation lead facilitates the CQI team meetings and presents the Step 4 reports to the CQI team. Program leadership share Step 4 report findings with frontline staff in staff meetings.	CQI team members (program director, program manager, evaluation lead, data manager(s)); program staff (case managers, facilitators, recruitment and retention specialists) who are able to 1) provide feedback on challenges and successes with the implementation of the intended intervention, 2) see the results of the intervention
Relationship skills workshops	Healthy relationships curriculum (TYRO Core Communication; TYRO Leadership)	A total of 18 hours, with six two-hour sessions occurring weekly (TYRO Leadership) plus two three-hour sessions occurring weekly (TYRO Core Communication)	Group lessons provided online via Zoom or in-person at service sites; two trained facilitators lead every session	Individuals in the greater Dallas-Fort Worth area with low income

**Table 2.** Staff education and training (initial and ongoing)

Component	Education and initial training	Ongoing training
Relationship skills workshop	All facilitators, case managers, intake specialists, and other members of the staff must complete the workshop as a participant before entering the certified TYRO Facilitator training component. Once the training is complete, each facilitator observes an experienced staff	Facilitators complete an annual refresher process to ensure curriculum fidelity. That process includes observations by the Program Manager, Program Director, or another qualified designee. We attempt to provide opportunities to become re-certified every two to three years. Other

Component	Education and initial training	Ongoing training

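### RQ2 reads improvement at site-metrics targeted for falling short, and no baseline is designated that leaves out the data that triggered the targeting

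*Protocol*

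**What the plan says.** - **Question.** Protocol, Outcomes study, section 1: RQ2 asks "Did meaningful improvements in primary workshop dosage, survey response rates, or program attrition rates vary by service site", restricted to sites that worked on the same metric.
- **Selection.** Protocol, Outcomes study, section 4: "metrics that are already at or close to targets are not selected for intervention". Neither the targets nor the meaning of close is given as a number. The Step 2 report is "prepared and presented annually in quarter 2 of each grant year by evaluation lead" and is meant to "target improvement efforts by setting site-specific priorities for interventions". Step 3 is meant to "establish a performance intervention agenda for each site".
- **One data source.** Protocol, Outcomes study, section 3: nFORM administrative data feed the yearly site-level reports and are also the source of the RQ2 outcomes.
- **Reading of the result.** Section 4 will judge "whether performance targets were reached and whether improvements were meaningfully large" after the strategies are in place. The Step 4 report, "prepared annually in quarter 4 of each grant year by evaluation lead", compares each site before and after. The SAP (Analytic approach) plots monthly enrolment cohorts since program start with interventions marked. It looks for site-level improvement both since program start and right after each intervention, and says in advance that improvement is expected in both. No test, interval or caveat is planned for RQ2.
- **Baseline.** Section 4 promises baseline data for each targeted metric as a way of dealing with ceiling and floor effects. No window is defined.
- **Dates.** Protocol, Implementation study, section 3: the site and the cohort or date of each intervention are logged, and so is the delivery date of each report.

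**The concern.** A site's observed rate in a given period is its underlying rate plus chance. If a site-metric is targeted because the observed value was poor, chance on average made it look worse than it is. The next period will then tend to look better even if the intervention did nothing. A before/after change that starts from the triggering data contains this rebound.

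The plan expects improvement immediately after interventions, so a chance rebound has the pattern that would be taken as success. With no denominators or intervals planned, a reader of the graphs could not tell the two apart. The judgements most exposed are whether a target was reached and whether a gain was meaningfully large. The comparison between sites is exposed through site size, because smaller windows rebound more.

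**Working it through.** The plan has no figure to reproduce here: the sample size of 800 comes without a derivation, and RQ2 has no effect size or test.

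**Window sizes from the protocol.** Enrolment runs from 22 April 2021 to 15 February 2025: 1395 days, or 3.82 years. Ten locations are listed, and they varied over time.
- Ten active sites: 800 / 3.82 / 10 = 20.9 participants per site-year.
- Five active sites: 800 / 3.82 / 5 = 41.9.

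These are averages; actual cohorts will be uneven.

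**Assumptions (not in the documents).** Mean attrition 25%; a site is targeted if its observed attrition exceeds 25%; between-site SD of true rates 5, 10 or 15 points; no CQI effect; stable true rates; independent windows of equal size; baseline = the triggering window. Gain means the fall in attrition.

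**Hand approximation.** With SE² = 0.25 × 0.75 / n, selection above the mean gives an expected rebound of 0.798 × SE² / √(SD² + SE²).
- n = 21: SE² = 89.3 squared points. Rebound = 0.798 × 89.3 / 10.69, / 13.76 and / 17.73 = 6.7, 5.2 and 4.0 points.
- n = 42: SE² = 44.6. Rebound = 0.798 × 44.6 / 8.34, / 12.02 and / 16.42 = 4.3, 3.0 and 2.2 points.

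**Simulation (beta site rates, binomial windows, 1,000,000 draws).** The values at 21 exceed the approximation because counts are whole numbers: exceeding 25% of 21 needs at least 6, which is 28.6%.

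| Spurious gain, points | SD 5 | SD 10 | SD 15 |
|---|---|---|---|
| 21 per window | 7.7 | 5.9 | 4.4 |
| 42 per window | 4.4 | 3.1 | 2.2 |
| 84 per window | 2.9 | 1.7 | 1.2 |
| Baseline window not used for selection | 0.0 | 0.0 | 0.0 |

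**Sensitivity.**
- Thresholds of 20% to 30%: 3.5 to 10.5 points at 21, and 1.7 to 6.7 at 42.
- Threshold 10%, so that most site-metrics miss target: under 2 at 21, and under 1 at 42.
- Reports that accumulate data, 21 per site-year: 7.7/5.9/4.4 at the first review, falling to 3.2/2.1/1.5 at the third.
- A different set-up (success rates, assumed target 90%, selection below 85%, mean rate 75% to 90%, 5 to 40 per window): 1.2 to 14.3 points, positive in every scenario, and zero within 0.1 with an independent baseline.

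**Site size.** A site with 10 per window shows 6.7/6.5/5.6 points more spurious gain than one with 42. Both sizes are assumed.

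**What a selection-free window costs.** Assume 13 weeks from report to intervention; the documents give no delay. The window then holds 20.9 × 13/52 = 5.2 or 41.9 × 13/52 = 10.5 participants. The workshops are six plus two weekly sessions, so eight weeks if run in sequence. Leaving out partly exposed cohorts gives 20.9 × 5/52 = 2.0 or 41.9 × 5/52 = 4.0.

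The 95% half-width of a change is 1.96 × √(0.1875 × (1/a + 1/b)):
- 5 before and 21 after: 42 points; pooled over five sites, 42.2 / √5 = 19.
- 10 before and 42 after: 30 points; pooled, 29.9 / √5 = 13.

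At 21 per window, the single-site root mean squared error is about 14 points from the trigger window, against 22 to 23 from a gap window of 5. Pooled over five sites it is 9.4/8.3/7.6 against about 10. Trigger and gap data together give 8.2/7.4/6.9, but bias remains: 21/26 × 7.7 = 6.2 down to 21/26 × 4.4 = 3.6 points.

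**The case against.** **The clean months are already on the graphs.** The SAP plots every month since program start and marks the interventions, so any cohorts between report and intervention are displayed. This stands against a reading that no selection-free data exist. It does not settle the point: no such window is designated as the baseline, and the separate reading immediately after intervention is untouched.

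**RQ2 asks whether improvement varied between sites.** A rebound common to all targeted sites largely cancels in that contrast. This stands. What remains comes mainly from unequal site sizes, which the documents do not give. It does not protect the readings on targets reached and on meaningfully large gains.

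**RQ2 is descriptive, and the SAP speaks of association.** True, and this limits the severity. But the plan still draws judgements from the change and offers nothing to temper them.

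**The cure may be worse than the disease.** This stands against using only the gap window, as the errors above show. It supports showing both baselines.

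**The figures are for a binary rate.** Dosage is a mean percentage and may regress less. This stands.

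**Partial exposure may not arise.** Interventions can be logged by cohort, and those need not straddle a date. This stands; the issue is confined to interventions logged by date.

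**It is late.** The SAP is dated 4 September 2024, 1231 of 1395 days (88%) into enrolment, with data reviewed every two weeks. A minimum window size could hardly be called pre-specified now, and the fix does not rely on one.

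**Conclusion.** The concern holds in a limited form. Selection on an observed shortfall, outcomes from the same series, and no designated baseline free of the selection data mean that RQ2's before/after reading leans towards improvement, to the extent that the baseline includes the triggering data. The direction is clear. The size is not, because targets, site rates, site sizes and report look-back are not given. Under the stated assumptions it is about 4 to 8 points at 21 per window and 2 to 4 at 42, and under 2 at either size if most site-metrics miss target. Clustering within workshop cohorts was not modelled.

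Three stronger readings are not supported:
- **That observed improvements are artefacts.** The calculation shows what could appear with no effect, not that there was none.
- **That earlier data are biased the other way because they passed a previous review.** The protocol says that metrics near target are not selected; it does not say that every shortfall is. If every shortfall were targeted, a window that passed review would give about -7 to -8 points at 21. If half or a third were targeted at random, that shrinks to about -1 to -2.
- **That sites targeted on another metric are a clean control.** Attrition is defined by hours completed, dosage counts hours, and the exit survey is given at the final session, so an intervention on one can move the others.

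**What to change.** In the SAP's Analytic approach for RQ2:

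1. For each targeted site-metric, report the before/after change with denominators and 95% intervals, by site and pooled over sites that targeted the same metric.
2. Show the change against two baselines side by side: all pre-intervention cohorts, including the trigger period; and only cohorts enrolled after the triggering report and before the logged intervention. State that the first is biased towards improvement. State that the second is unbiased if true site rates are stable, but very imprecise and possibly empty. If rates drift and revert, 0.5 to 1.4 points of spurious gain remained in the drift scenarios simulated. The log does not list each report's data cut-off; its delivery date can stand in, at the price of a shorter window.
3. Where an intervention is logged by date and not by cohort, flag cohorts with sessions on both sides of that date.
4. State that improvement after intervention at selected site-metrics, or reaching target, is not by itself evidence of a CQI effect. Do not rank sites by gain without regard to their size.

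The cost is SAP wording and modest programming. No new data are needed, since the dates are logged and client-level data are exported. The price is wide intervals, and some sites will have no interpretable change.
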